Duration of Subject Participation:	Duration of treatment with The MetaNeb® System will be a minimum of 48 hours, or until the subject is discharged from the hospital (if discharge is earlier). Enrolled subjects will remain in the study through Day 4 or until the subject is discharged from the hospital, whichever occurs sooner.
Number of Subjects:	Up to approximately fifteen (15) subjects will be enrolled.
Study Population:	Post-surgical (thoracic, cardiac or abdominal surgery) non-mechanically ventilated patients with significant atelectasis, as documented by chest x-ray results.
Inclusion Criteria	
Patients who meet all of the following inclusion criteria and no exclusion criteria will be included in the study:
 
 • Post-surgical (thoracic, cardiac or abdominal surgery) • Age \geq 18 years • Significant atelectasis by chest x-ray • Patient meets indication for therapy intervention as defined by Recruitment and Airway Clearance Protocol (Respiratory Department Policy and Procedure) • Signed informed consent

Hill-Rom®	Evaluation of The MetaNeb® System to reduce atelectasis as assessed by chest x-ray	Page 8 of 29		
	CBI	06 March 2017	Rev C	CR-RR2016- 001

Exclusion Criteria:	
Patients who meet one or more of the following exclusion criteria will not be eligible for the study:
 
 • Cause of atelectasis suspected to be infectious or solid mass • Requirement for mechanical ventilation • Requirement for chronic supplemental oxygen • Hemodynamically unstable, as defined by need for vasopressor therapy • Anticipated need for mechanical ventilation or other poor clinical outcome, unrelated to atelectasis or secretion retention • Contraindication to MetaNeb® therapy (untreated tension pneumothorax) • Inability to perform MetaNeb® therapy using a mouthpiece • Anticipated hospital discharge within 24 hours

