Methods:	
Post-surgical patients with significant atelectasis confirmed by chest x-ray who require intervention and provide informed consent will be enrolled in the study. After enrollment, patients will be treated with The MetaNeb® System per a defined treatment regimen and within the approved product labeling. Details regarding therapy with The MetaNeb® System will be recorded.
 
After collection of the baseline chest-ray, chest x-rays during the treatment period will be assessed starting with Day 1 (approximately 24 hours) after initiation of treatment with The MetaNeb® System. In the case multiple chest x-rays are performed on a single day, the one closest to 24 hours from the previous day's chest x-ray will be used for study purposes.
 
Chest x-ray files will be sent to designated readers who are blinded to subject protected health information and/or date and time of chest x-ray. Chest x-rays will be scored using the Kelly atelectasis score. Chest x-rays will also be assessed using a comparative scale to evaluate intra-patient changes over time.
 
Any device related adverse events which occur after study enrollment and initial MetaNeb® therapy will be recorded.

Hill-Rom®	Evaluation of The MetaNeb® System to reduce atelectasis as assessed by chest x-ray	Page 9 of 29
	CBI	06 March 2017

Subject Withdrawal:	
Subjects may withdraw consent to participate in the study at any time. The subject may also be withdrawn from the study according to investigator judgement regarding the continued health or safety of the subject or related to inability or unwillingness to perform study therapy or procedures.

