3.1 Overview of Study Design

3.1.1 Design:

The study will be a non-randomized open label study. It is a pre-post study design with subjects serving as their own control. All subjects will receive treatment with The MetaNeb® System. The study will be conducted at one (1) site in the US.

The study will evaluate the impact of the therapy on chest x-ray scores and related clinical endpoints. Patients with evidence of significant atelectasis on chest x-ray will be enrolled. After assessing baseline status, therapy with The MetaNeb® System will be introduced and incorporated into the respiratory care treatment regimen. Outcomes will be assessed at regular intervals following the initiation of the therapy.

3.1.2 Procedure:

Up to approximately fifteen (15) patients will be recruited and enrolled from the ICU and/or general care floors. Eligible subjects will be patients who are not intubated, and who have developed clinically significant atelectasis (i.e. described in the radiologist report). Demographic data will be collected from the medical record of each subject at the time of enrollment.

Following enrollment in the study, subjects will receive treatment with The MetaNeb® System per a defined treatment regimen and within the approved product labeling. Treatments will be delivered on a defined schedule. Enrolled subjects will be treated for a minimum of 48 hours, or until discharge (if discharge from the hospital occurs before 48 hours).

Chest x-ray files at baseline (Day 0), for enrolled subjects, will be collected. Daily chest x-ray files for Day 1 (approximately 24 hours), Day 2 (approximately 48 hours) and Day 4 (approximately 96 hours) or discharge (if discharge occurs before Day 4) will be collected as they become available.

All chest x-rays will be logged by subject number, date and time, and event (i.e. Day 0, Day 1 and Day 2, Day 4/discharge) and assigned a number from a random number list. All chest x-rays, identified only by the assigned number will be placed in a file for review and scoring by the blinded radiologist(s).

Pulse Oximetry SpO₂ data along with the subject's oxygen support status (O₂ delivered in LPM or %) from the time corresponding to the baseline and the Day 4/discharge

Hill-Rom®	Evaluation of The MetaNeb® System to reduce atelectasis as assessed by chest x-ray		
	CBI	06 March 2017	Rev C

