3.4 Study Observations Table

The study observations and documentation timeline is outlined in Table 1.

Hill-Rom®	Evaluation of The MetaNeb® System to reduce atelectasis as assessed by chest x-ray		
	CBI	06 March 2017	Rev C

Table 1. Study Observations

Day	Day 0 (Treatment Initiation)	Day 1 (Post Treatment Initiation)	Day 2 (Post Treatment Initiation)	Day 4 / Discharge (or Early Termination)
Selection Criteria / Enrollment	X			
Informed Consent	X			
Demographic Data	X			
Medical History	X			
Chest X-ray Score (Kelly)	X (Baseline)	X	X	X
Chest X-ray Ranking (Comparative)				X
O2 Requirement Collected at time of Baseline and Day 4 / Discharge Chest X-rays.				
Collected at beginning of each shift for Day 1 and Day 2	X	X	X	X
SpO ₂ Collected at time of Baseline and Day 4 / Discharge Chest X-rays.				
Collected at beginning of each shift for Day 1 and Day 2	X	X	X	X
Borg Dyspnea Scale	X	X	X	
Respiratory Status Evaluation	X		X	
MetaNeb Treatments	X	X	X	X
Study Exit Form				X

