3.5 Statistical Methods and Analysis

3.5.1 Sample Size Estimation:

The sample size for this study is a convenience sample. The study is designed to provide preliminary information on the benefits of the addition of the MetaNeb® System in treating pulmonary atelectasis and associated hypoxemia. Resulting data on the outcomes associated with The MetaNeb® System may help to provide definition of the effect size and variability and the number of subjects required for subsequent studies.

Subjects with a Kelly Score of one (1) or less in both lungs on the baseline (Day 0) chest x-ray will be excluded from the primary endpoint analysis and secondary endpoint analyses related to Kelly Score.

3.5.2 Statistical Analysis:

- Summary statistics and data listings will be provided.
- Demographic data will be summarized. For continuous type data (e. g. Age), descriptive summary statistics (N, mean, median, standard deviation, min, and max) will be presented. For categorical variables (gender, race, etc.) the number and percent of patients in each category will be provided.

Primary Endpoint:

The Kelly atelectasis score at Day 2 will be summarized with shift tables from baseline. Proportion of subjects showing an improvement from baseline will be summarized.

Secondary Endpoints:

- The Kelly atelectasis score at Day 1 and Day 4/discharge will be summarized with shift tables from baseline.
- Time to a Kelly score of 1 in both lungs will be summarized with a Kaplan-Meier curve, with estimate of the median time and a 95% confidence interval.
- To address possible decrease in sample size over time, due to subjects' improvement and stoppage of use of The MetaNeb® System, the Kelly atelectasis score shift from baseline will also be tabulated using LOCF (last observation carried forward).
- Patient reported level of dyspnea (modified Borg dyspnea scale) will be tabulated for each time point.
- The oxygenation index will be summarized by calculating the mean and standard deviation at each time point, as well as for changes from baseline.

Hill-Rom®	Evaluation of The MetaNeb® System to reduce atelectasis as assessed by chest x-ray		
	CBI	06 March 2017	Rev C

- Chest x-ray improvement using a comparative scale after a minimum of forty-eight (48) hours of therapy with The MetaNeb® System
- Oxygenation index (SpO₂/FiO₂ ratio) at Day 1 and Day 4/discharge compared to baseline
- Change in patient respiratory status (Borg Dyspnea Scale – Appendix 2)

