5.2 Complaints and Adverse Events Reporting

Hill-Rom®	Evaluation of The MetaNeb® System to reduce atelectasis as assessed by chest x-ray	Page 20 of 29
CBI	06 March 2017	Rev C

During the study, any adverse device effect, device-related complaint or allegation of injury (of any type) must be reported to the Sponsor within 24 hours. Please contact [name] by [contact] (office) PI [REDACTED] or email: [contact].

A complaint is defined as any written, electronic or verbal communication that alleges deficiencies related to the identity, design, quality, durability, reliability, safety, effectiveness or performance of the device. A serious injury is defined as an injury or illness that is life-threatening; results in permanent impairment of a body function or permanent damage to a body structure; or necessitates medical or surgical intervention to preclude permanent impairment of a body function or permanent damage to a body structure.

Any device complaint and/or allegation of injury shall be reviewed, evaluated, and investigated by Hill-Rom Post Market Surveillance and reported to the appropriate Health Authority per current regulations. The Investigators are responsible for informing the Institutional Review Boards, as per their guidelines.

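### The withdrawal rule lets a subject who stops therapy for safety or intolerance leave the whole study, and no observation is then required through Day 4 or discharge

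*Combined protocol and SAP*

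**What the plan says.** **Leaving the study.** The Subject Withdrawal entry of the Synopsis lets subjects withdraw consent at any time and adds: "The subject may also be withdrawn from the study according to investigator judgement regarding the continued health or safety of the subject". It continues: "or related to inability or unwillingness to perform study therapy or procedures". Both grounds lead out of the study, not only off the device. The body of the protocol has no withdrawal section of its own.

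**Intended observation.** The Synopsis entry on duration says: "Enrolled subjects will remain in the study through Day 4 or until the subject is discharged from the hospital, whichever occurs sooner". Treatment has a shorter minimum in section 3.1.2: "Enrolled subjects will be treated for a minimum of 48 hours, or until discharge". Observation is therefore meant to be able to outlast therapy.

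**Last assessment.** The final column of Table 1 is headed "Day 4 / Discharge (or Early Termination"). It carries the Kelly score, film ranking, oxygen requirement, SpO2, treatments and the exit form. It has no entry for the Borg scale or the Respiratory Status Evaluation.

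**Analysis.** Section 3.5.2 expects the sample to fall over time "due to subjects' improvement and stoppage of use of The MetaNeb® System", and adds a last-observation-carried-forward (LOCF) tabulation of the Kelly shift.

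**Safety.** The Synopsis says: "Any device related adverse events which occur after study enrollment and initial MetaNeb® therapy will be recorded". Section 5.2 requires that, during the study, "any adverse device effect, device-related complaint or allegation of injury (of any type) must be reported to the Sponsor within 24 hours". Section 6.1 asks for more detailed follow-up reports on serious and unanticipated device effects if further information emerges.

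**The concern.** Subjects who stop because of a health or safety concern, or because they cannot manage the therapy, are plausibly not a random subset. If they leave the study when they stop, the remaining films and oxygenation values come mainly from subjects who tolerated the device. In an open-label, single-arm, pre-post study no comparison group would reveal that selection. Section 3.5.1 says the results may help define effect size and variability for later studies, so any resulting optimism could carry forward into their planning.

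The plan leaves this to individual judgement. Two investigators facing the same subject could both follow the protocol, one keeping the subject under observation and the other completing the exit form.

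**Working it through.** The plan states no power, withdrawal rate or expected response that could be reproduced. The check is therefore a reading of the text followed by an illustration.

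**1. What is required for a subject withdrawn at, say, hour 30**

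| Item | Requirement after withdrawal |
|---|---|
| Day 2 Kelly score (primary) | None. The early-termination film precedes Day 2 |
| Day 4 Kelly score | None beyond the early-termination film |
| SpO2 and oxygen support | One early-termination reading, then nothing scheduled |
| Borg scale, Respiratory Status Evaluation | Not in the early-termination column. Section 3.4.1 brings them forward only for hospital discharge |
| Device-related events | Recording has a stated start and no stated end. The section 5.2 duty applies during the study. Neither says whether a withdrawn subject is covered |

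LOCF does not fill the gap. It is an additional tabulation of the Kelly shift only, and it carries the last film forward, so it cannot show change in either direction after withdrawal.

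**2. How far the Day 2 proportion could move**

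Inputs:
- N = 15, the approximate maximum in the Synopsis. Section 3.5.1 removes subjects with a baseline Kelly score of 1 or less in both lungs, so the real denominator may be smaller.
- Assumed: w subjects withdrawn before Day 2, and x of the remaining 15 − w improved, with x set near 70%.
- Intervals are Clopper-Pearson 95%. The plan specifies 95% but names no method.

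Formulas: observed = x/(15 − w); none of the withdrawn improved = x/15; all of them improved = (x + w)/15.

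| w | Observed (95% CI) | None improved (95% CI) | All improved |
|---|---|---|---|
| 1 | 10/14 = 71.4% (41.9 to 91.6) | 10/15 = 66.7% (38.4 to 88.2) | 11/15 = 73.3% |
| 2 | 9/13 = 69.2% (38.6 to 90.9) | 9/15 = 60.0% (32.3 to 83.7) | 11/15 = 73.3% |
| 3 | 8/12 = 66.7% (34.9 to 90.1) | 8/15 = 53.3% (26.6 to 78.7) | 11/15 = 73.3% |

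The gap between the two extremes is w/15: 6.7, 13.3 and 20.0 percentage points for one, two and three losses. With three losses, the observed figure exceeds the none-improved figure by 66.7 − 53.3 = 13.3 points before rounding. Neither the Synopsis nor section 3.5.2 says which denominator applies.

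**3. How likely any loss is**

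P(at least one withdrawal among 15) = 1 − (1 − d)^15. For assumed rates d of 5%, 10% and 20% this is 53.7%, 79.4% and 96.5%.

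**The case against.** A reader might infer that stopping therapy automatically ends participation. The documents do not say so. The withdrawal wording is permissive and rests on investigator judgement. The duration text does not make observation conditional on continued therapy. Section 3.1.4 has exceptions to the treatment protocol recorded, which allows a subject to depart from the regimen and stay in.

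A reader might also infer that safety information stops when a problem appears. That is not supported either. An event that prompts withdrawal is still recorded, reported within 24 hours and counted in the incidence table, which covers the study as a whole. Serious and unanticipated device effects also call for further reports as information emerges.

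Section 3.5.2 links stoppage to improvement, so it is not evidence that subjects who stop because of harm are dropped. Films are logged by date, time and event, and nothing says that an early-termination film will be analysed as Day 4. Unwillingness to perform procedures need not reflect harm. That withdrawn subjects are those most likely to have been harmed is an inference from the grounds for withdrawal, not something the plan shows.

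Finally, this is a small, preliminary, descriptive study of a marketed device. The consent pages are not available, so whether consent already covers data collection after withdrawal cannot be judged.

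These points stand, and they limit the claim. They do not close the gap. Discretion leaves continued observation to case-by-case choice, the reporting duties do not require anyone to keep looking, and none of them supplies a Day 2 film.

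**Conclusion.** The point holds in a limited form. The plan does not separate stopping the device from leaving the study. Once a subject is withdrawn for safety or intolerance, it requires no film, oxygenation reading or safety follow-up beyond one final assessment. A subject withdrawn before Day 2 is lost to the primary endpoint, and the Day 2, Day 4 and oxygenation summaries may lean towards subjects who tolerated the device.

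The size depends on a withdrawal rate that the documents do not give. Under the assumptions above, one to three losses leave the Day 2 proportion uncertain by about 7 to 20 percentage points. That is less than the sampling uncertainty at this sample size. Unlike sampling error, however, it could lie mainly in one direction and would not be visible in the reported interval. The direction rests on the assumption that withdrawn subjects did worse.

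**What to change.** 1. In Subject Withdrawal, define two states: stopping study therapy, and withdrawing consent to data collection. A subject who stops therapy without withdrawing that consent stays in the study.
2. For such subjects, continue to abstract routine chest films, SpO2, oxygen support and device-related events from the hospital record through Day 4 or discharge.
3. Record the date and reason for stopping therapy on the exit form.
4. Label early-termination films by their actual study day, and align the Table 1 heading.
5. Reword section 3.5.2 so that stopping the device is not itself a cause of missing data, and state the denominator used when a Day 2 film is still missing.

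When therapy should stop remains with the investigator and is not touched by this change.

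The cost is an amendment, with consent wording if needed, and a little extra chart abstraction for a few inpatients. The plan already draws these data from the hospital record, so no procedure is added. Results may look slightly less favourable.

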1.0 Introduction

1.1 Background and Significance

Post-operative pulmonary complications (PPC) are associated with significant excess morbidity, mortality and healthcare expenditure. Atelectasis is an important cause and critical component of PPC [2-4]. Hypoxemia is a strong indicator of the presence of atelectasis [3]. The presence, progression or resolution of atelectasis can be confirmed and quantified by radiologic assessment [5,6].

Evidence from previous studies suggests that atelectasis can be effectively prevented or treated by early intervention including, but not limited to, lung expansion (LE) techniques and secretion clearance [3,4,7,8]. Such interventions should significantly mitigate progression to serious PPC.

1.3 Rationale for the Proposed Study

Atelectasis is a complication in many hospitalized patients and is particularly common in patients recovering from cardiac and other thoracic and upper abdominal surgeries. It has been shown to be a precursor to other complications. The MetaNeb® System creates CPEP and CHFO for mobilization of secretions, lung expansion therapy, the treatment and prevention of pulmonary atelectasis. The proposed study is intended to evaluate the impact of this therapy in treating patients with significant atelectasis.

2.0 Study Objectives

The primary objective of this study is to evaluate the impact of use of The MetaNeb® System in clearance of atelectasis, as demonstrated by improvement in chest x-ray.

3.0 Study Design

Hill-Rom®	Evaluation of The MetaNeb® System to reduce atelectasis as assessed by chest x-ray	Page 12 of 29
CBI	06 March 2017	Rev C

3.1 Overview of Study Design

3.1.1 Design:

The study will be a non-randomized open label study. It is a pre-post study design with subjects serving as their own control. All subjects will receive treatment with The MetaNeb® System. The study will be conducted at one (1) site in the US.

The study will evaluate the impact of the therapy on chest x-ray scores and related clinical endpoints. Patients with evidence of significant atelectasis on chest x-ray will be enrolled. After assessing baseline status, therapy with The MetaNeb® System will be introduced and incorporated into the respiratory care treatment regimen. Outcomes will be assessed at regular intervals following the initiation of the therapy.

3.1.2 Procedure:

Up to approximately fifteen (15) patients will be recruited and enrolled from the ICU and/or general care floors. Eligible subjects will be patients who are not intubated, and who have developed clinically significant atelectasis (i.e. described in the radiologist report). Demographic data will be collected from the medical record of each subject at the time of enrollment.

Following enrollment in the study, subjects will receive treatment with The MetaNeb® System per a defined treatment regimen and within the approved product labeling. Treatments will be delivered on a defined schedule. Enrolled subjects will be treated for a minimum of 48 hours, or until discharge (if discharge from the hospital occurs before 48 hours).

Chest x-ray files at baseline (Day 0), for enrolled subjects, will be collected. Daily chest x-ray files for Day 1 (approximately 24 hours), Day 2 (approximately 48 hours) and Day 4 (approximately 96 hours) or discharge (if discharge occurs before Day 4) will be collected as they become available.

All chest x-rays will be logged by subject number, date and time, and event (i.e. Day 0, Day 1 and Day 2, Day 4/discharge) and assigned a number from a random number list. All chest x-rays, identified only by the assigned number will be placed in a file for review and scoring by the blinded radiologist(s).

Pulse Oximetry SpO₂ data along with the subject's oxygen support status (O₂ delivered in LPM or %) from the time corresponding to the baseline and the Day 4/discharge

Hill-Rom®	Evaluation of The MetaNeb® System to reduce atelectasis as assessed by chest x-ray		
	CBI	06 March 2017	Rev C

chest x-rays will be collected. SpO₂/FiO₂ ratio will be calculated based on pulse oximetry and oxygen support corresponding to the time of each chest x-ray.

Pulse Oximetry SpO₂ data along with the subject's oxygen support status will also be collected from the patient record at the time closest to the beginning of each shift, for Day 2 and Day 3. SpO₂/FiO₂ ratio will be calculated based on pulse oximetry and oxygen support corresponding to the time closest to the beginning of each shift.

A timeline showing data procedures and collection points is included as Table 1 Study Observations Table.

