3.3 Evaluation Criteria/Effectiveness

The therapy regimen (treatment with The MetaNeb® System) will be evaluated to determine if there is an improvement in chest x-ray scores after initiation of the therapy. The study will also evaluate if there is a corresponding improvement in the clinical respiratory status of the patients demonstrated by a decrease in the O₂ requirement and/or an improvement in oxygen saturation. Endpoints are described below:

Primary Endpoint:

Chest x-ray score improvement at Day 2 (approximately 48) hours after initiation of therapy with The MetaNeb® System.

Chest x-rays will be scored using the Kelly scoring system (Appendix 1) to assess the presence of atelectasis on Day 2, after initiation of therapy with The MetaNeb®

Hill-Rom®	Evaluation of The MetaNeb® System to reduce atelectasis as assessed by chest x-ray			Page 15 of 29
	CBI	06 March 2017	Rev C	CR-RR2016- 001

System. Scores for chest x-rays at Day 2 will be compared to the scores for chest x-rays taken at baseline. The Kelly score for each of the chest x-rays will be assessed by blinded reader.

The baseline chest x-ray for each subject is the qualifying x-ray that determined the presence of significant atelectasis.

Secondary Endpoint(s):

- Chest x-ray score improvement at Day 1 (approximately 24 hours) and at Day 4 (approximately 96 hours or at discharge, if discharge occurs before Day 4) after initiation of therapy with The MetaNeb® System.

Scored using the Kelly score, as described above, to assess the presence of atelectasis.

- Chest x-ray improvement using a comparative scale after a minimum of forty-eight (48) hours of therapy with The MetaNeb® System.

Chest x-ray improvement assessed using a comparative scale for baseline, Day 1, Day 2 and Day 4/discharge. Four chest x-rays for each enrolled subject (baseline, Day 1, Day 2 and Day 4/discharge), with date and time masked, will be sent to the radiologist for comparison. The radiologist will rank the four x-rays 1, 2, 3 or 4 (1 = least atelectasis, 4 = most atelectasis).

- Oxygenation index ($\text{SpO}_2/\text{FiO}_2$ ratio) at Day 1, Day 2 and Day 4/discharge compared to baseline
- Patient reported level of dyspnea (assessed by Modified Borg Dyspnea Scale – Appendix 2)
- Change in patient respiratory status (Respiratory Status Evaluation – Appendix 3)

Physician observation and evaluation of patient respiratory status at time of enrollment (baseline) and on Day 2

Safety:

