3.4.1 Study Observations Table Detailed Description

Documentation of observations will be completed by study staff at the time of occurrence, from review of the patient's medical records and from scores and rankings for chest x-rays completed by radiologist review. A detailed description of documentation requirements for each parameter is below.

Demographic Data: The following data will be recorded from the patient medical record: Age, Height, Weight, Race and Ethnicity, Gender.

Medical History: Admitting diagnosis, pulmonary history will be recorded from the patient medical record including: Asthma, CF, Bronchiectasis, COPD, Neuromuscular Disease, Obstructive Sleep Apnea or Other Pulmonary Condition(s).

Hill-Rom®	Evaluation of The MetaNeb® System to reduce atelectasis as assessed by chest x-ray		
	CBI	06 March 2017	Rev C

Chest X-ray Score (Kelly): Chest x-ray files will be collected beginning with the enrollment chest x-ray (Day 0) and for Day 1, Day 2 and Day 4 or at time of discharge from the hospital (if earlier). All chest x-rays will be logged by subject number, date and time, and event (i.e. Day 0, Day 1, Day 2, Day 4/discharge) and assigned a number from a random number list. All chest x-rays, identified only by the assigned number, will be placed in a file and then reviewed and scored by the radiologist(s). Radiologist(s) will be blinded to subject and event.

Chest X-ray Ranking (Comparative): Chest x-ray files will be collected for each subject beginning with the enrollment chest x-ray (Day 0) and for Day 1, Day 2, and Day 4 or at time of discharge from the hospital (if earlier). The random number assigned to each chest x-ray (Day 0, Day 1, Day 2, Day 4) will be used to identify the time and date. The group of chest x-rays for each subject, identified only by the assigned number, will be placed in a file and then reviewed, compared and ranked by the radiologist(s). Radiologist(s) will be blinded to subject and event.

O₂ Requirement: The oxygen support status for each subject will be recorded for the time of the baseline and Day 4/discharge chest x-rays. The oxygen support status will also be recorded for the beginning of each shift for Day 1 and Day 2.

SpO₂: The oxygen saturation (based on pulse oximetry readings) for each subject will be recorded for the time of the baseline and Day 4/discharge chest x-rays. The oxygen saturation will also be recorded for the beginning of each shift for Day 1 and Day 2.

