SpO₂/FiO₂ Ratio: The SpO₂/FiO₂ ratio (based on pulse oximetry readings and the O₂ requirement) for each subject will be calculated for the time of each chest x-ray. The SpO₂/FiO₂ ratio will also be calculated for the beginning of each shift for Day 0 – Day 2, or until the time of discharge from the hospital (if earlier).

Assessment of Dyspnea (Modified Borg Dyspnea Scale): An evaluation of each subject's dyspnea level will be assessed using patient response and a Modified Borg Dyspnea Scale. Evaluation will be completed by respiratory staff at the time of enrollment into the study (Day 0), and on a daily basis for Day 1 and Day 2, or at the time of discharge from the hospital (if earlier).

Respiratory Status Evaluation: An evaluation of each subject's respiratory status will be completed by the physician investigator at the time of enrollment into the study (Day 0) and on Day 2, or at the time of discharge from the hospital (if earlier).

MetaNeb® Treatments: All MetaNeb® treatments will be documented for each day beginning with enrollment (Day 0), Day 1 and Day 2, and through Day 4 or until the time of discharge from the hospital (if earlier).

Hill-Rom®	Evaluation of The MetaNeb® System to reduce atelectasis as assessed by chest x-ray		Page 18 of 29
	CBI	06 March 2017	Rev C

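### The SpO₂/FiO₂ ratio is due at all four chest x-rays, but its inputs are listed for film-time collection only at baseline and Day 4/discharge

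*Combined protocol and SAP*

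**What the plan says.** **Where the ratio is required.** Section 3.1.2 (Procedure) states: "SpO₂/FiO₂ ratio will be calculated based on pulse oximetry and oxygen support corresponding to the time of each chest x-ray". Section 3.4.1, under the ratio's own entry, says that it "for each subject will be calculated for the time of each chest x-ray". Section 3.3 fixes the number of films: "Four chest x-rays for each enrolled subject (baseline, Day 1, Day 2 and Day 4/discharge"). The same section lists the oxygenation index as a secondary endpoint "at Day 1, Day 2 and Day 4/discharge compared to baseline".

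**What is collected at film time.** Section 3.1.2 takes SpO₂ and oxygen support "from the time corresponding to the baseline and the Day 4/discharge" films. Table 1 says of each item: "Collected at time of Baseline and Day 4 / Discharge Chest X-rays". Section 3.4.1 says: "The oxygen support status for each subject will be recorded for the time of the baseline and Day 4/discharge chest x-rays". Its SpO₂ entry has the same limit: the saturation "for each subject will be recorded for the time of the baseline and Day 4/discharge chest x-rays".

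**What else is collected.** The only other planned readings are at shift starts. Table 1 and section 3.4.1 place them on Day 1 and Day 2, whereas section 3.1.2 places them on Day 2 and Day 3. The ratio entry in section 3.4.1 calls for shift-start ratios from Day 0 to Day 2.

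**How it is analysed.** Section 3.5.2 summarises the index by mean and standard deviation at each time point and for changes from baseline.

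**The concern.** The calculation rule and the collection rule do not match. Staff who follow the collection text would not record the two inputs at the Day 1 and Day 2 films, and Day 2 is the time of the primary x-ray comparison.

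The change-from-baseline summary needs one defined value per subject at each time point. Baseline and Day 4/discharge have one film-time value each. Day 1 and Day 2 have, at best, several shift-start values and no rule for choosing or averaging them, so the choice could be made after the data are seen. Section 3.1.4 leaves oxygen to the care team's routine prescription, so the ratio can move between a shift start and a film for reasons unrelated to the state of the lung. A film-time baseline set against a shift-start follow-up value adds that variation to the change.

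Section 3.5.1 says the data may help define effect size and variability for later studies, so a consistently timed measure has some value here even though nothing is tested.

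**Working it through.** The plan states no figure to reproduce: the sample is a convenience sample, and no power or precision is given for this endpoint. The check sets what is required beside what is collected, then counts.

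| Time | Film-time ratio required (3.1.2, 3.4.1) | Film-time inputs listed (3.1.2, Table 1, 3.4.1) | Shift-start inputs, Table 1 and 3.4.1 | Shift-start inputs, 3.1.2 |
|---|---|---|---|---|
| Baseline (Day 0) | yes | yes | no | no |
| Day 1 | yes | no | yes | no |
| Day 2 | yes | no | yes | yes |
| Day 3 | no film | – | no | yes |
| Day 4/discharge | yes | yes | no | no |

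**Count.** Inputs: 4 films per subject (section 3.3), film-time inputs at 2 of them, and up to about 15 subjects (section 3.1.2).
- Required: 4 × 15 = 60 film-time ratios.
- Inputs listed for collection: 2 × 15 = 30.
- Not covered: 60 − 30 = 30, or 2 of 4 per subject.

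The 30 is a ceiling. Some films may not be available, and a film taken at a discharge on Day 1 or Day 2 would fall under the discharge rule and so have its inputs recorded.

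**Baseline on the shift-start scale.** The ratio entry in section 3.4.1 asks for shift-start ratios from Day 0, which could in principle supply a like-for-like baseline. The collection entries in the same section list shift-start readings only for Day 1 and Day 2, so the Day 0 inputs are not listed either.

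**Distance between a film and a shift start.** The documents give no shift length, so this is an assumption. For shifts of length L, films at random times and readings exactly at shift start, the mean distance to the nearest shift start is L/4 and the maximum is L/2.
- L = 8 h: mean 8/4 = 2 h, maximum 8/2 = 4 h; 24/8 = 3 readings per day.
- L = 12 h: mean 12/4 = 3 h, maximum 12/2 = 6 h; 24/12 = 2 readings per day.

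Section 3.1.2 accepts the charted value nearest to shift start, so actual gaps could be longer or shorter. These figures only illustrate scale.

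**The case against.** **'Each' may mean the two films just named.** In section 3.1.2 the calculation sentence directly follows the one naming the baseline and Day 4/discharge films, and the next paragraph has the same collect-then-calculate form. There the narrow reading is arguable. It is weaker in section 3.4.1, where the ratio has its own entry and is set for every film without qualification. The contradiction is therefore not removed.

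**The values may be in the chart.** Films are logged with date and time, and study data come partly from record review. This stands: a Day 1 or Day 2 film-time value may well be retrievable. The accurate statement is that the plan does not list it for collection, not that it does not exist.

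**The endpoint survives.** A reader might infer that there will be no Day 1 or Day 2 oxygenation data, or that the secondary endpoint cannot be estimated. The documents do not support that. Table 1 and section 3.4.1 collect both inputs at shift starts on both days, and section 3.3 names days, not film times, for this endpoint. What is lost is the film-time value and a common timing across visits.

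**No film-matched analysis is planned.** A reader might also take section 3.3's interest in oxygenation improving alongside the films to require a paired analysis at Day 2. It does not. Section 3.5.2 plans only summaries and changes from baseline, and the film times themselves are approximate.

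**Conclusion.** The plan contradicts itself. It calls for a film-time ratio at four films and lists the inputs for two. As written, the inputs for the Day 1 and Day 2 film-time ratios are not collected: 2 of 4 per subject, at most 30 of 60 if 15 subjects have all films.

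An oxygenation index on Day 1 and Day 2 can still be formed from shift-start readings under Table 1 and section 3.4.1, but with no rule for which reading represents the day and with a baseline timed differently. Under section 3.1.2's own schedule, Day 1 has no planned reading at all.

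The consequence is modest. It concerns a descriptive secondary endpoint in a convenience sample, and the Kelly primary endpoint is unaffected. The count rests on reading section 3.4.1 literally. The conclusion does not depend on any assumed shift length.

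**What to change.** 1. In section 3.1.2, Table 1 and the two input entries of section 3.4.1, list SpO₂ and oxygen support for recording from the chart at each study film: baseline, Day 1, Day 2 and Day 4/discharge.
2. In section 3.5.2, name the film-time ratio as the value used for each time point and for change from baseline.
3. Keep the shift-start readings as a separate descriptive profile.
4. Reconcile the shift-start days: Day 2 and Day 3 in section 3.1.2, Day 1 and Day 2 in Table 1 and section 3.4.1, and Day 0 to Day 2 for the ratio in section 3.4.1. Step 1 alone does not settle this.
5. At the same time, align the endpoint days: section 3.3 includes Day 2, but the ratio's own bullet in section 3.5.2 lists only Day 1 and Day 4/discharge.

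The cost is protocol and CRF wording plus two more chart values on each of two days, so 2 × 2 = 4 per subject. No new procedure is needed.

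The contradiction could also be removed by limiting the film-time ratio to the baseline and Day 4/discharge films and defining which shift-start reading stands for Day 1 and Day 2. That is workable, but it leaves the timing mixed unless a shift-start baseline is collected too. Recording at all four films is simpler.
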